The final SCP-R intervention included four sections for each of the four planned reproductive health issue (hot flashes, fertility-related concerns, vaginal symptoms and contraception) and an additional fifth issue on genetic cancer risk. For each issue, the four sections included: 1) a 1- to 2-page SCP framed in a question and answer format; 2) a detailed summary of the systematic review results with hyperlinks to primary research articles; 3) a summary of clinical guidelines with hyperlinks; 4) a list of curated web-based resources. This content was programmed into the study website. The intervention arm will be able to access all 4 sections for all 5 issues (Appendix A); the waitlist control arm will only be able to access the list of curated web-based resources for all 5 issues.

Website and text messaging platforms

We collaborated with an experienced web architect to develop a HIPAA-compliant website that enabled online participant registration, consent, completion of questionnaires, automated randomization and access to group-specific intervention material, integration with MOSIO, a text messaging software, and pairing of YBCSs with their nominated HCPs. The web portal is programmed to send study gift cards and weekly reminders on incomplete tasks to YBCS and HCP participants.

The text messaging platform is programmed to push daily text messages to all YBCS participants to ascertain hot flash frequency and severity. Natural language processing is embedded to minimize variation in how participants provide hot flash responses. In addition, biweekly text messages with reproductive health prompts will be sent to YBCS participants in the intervention arm, while biweekly study adherence text messages will be sent to YBCS participants in the waitlist control arm. The text messaging platform supports opt out by participants and two-way text messaging capabilities between participants and study staff.

This web- and text message-based design supports streamlined YBCS screening, consent, follow-up, and data collection, enables geographically diverse recruitment and utilizes fewer resources compared to a traditional in-person RCTs. Daily hot flash text messages will provide near real-time data collection to minimize recall bias.

YBCS eligibility, recruitment, consent and enrollment

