At enrollment, each YBCS participant nominates a HCP with whom they wish to discuss reproductive health issues. Study staff contact nominated HCPs by email, phone and/or fax for study recruitment. After five contacts, non-responsive HCPs are mailed the study consent, enrollment questionnaire and their patient's SCP materials. Interested HCPs are directed to the study web portal to create a secure personal account, followed by online access to study description, screening for eligibility and consent. Consented HCP participants complete the enrollment questionnaire and are provided with access to their patient's intervention materials, i.e. full SCP-R or only curated web-based resource lists. HCPs will complete a 24-week questionnaire and may opt to complete all study procedures (consent, questionnaires) and access intervention materials in a paper format.

Blinding

Study staff and YBCS and HCP participants are blinded to treatment allocation. Automated computer allocation of participants into intervention or waitlist control arm within the study portal allow for study staff to be blinded to assignment. YBCS and HCP participants are informed about participant randomization in the trial but are not notified of assignment until they complete their final study tasks. YBCS and HCP participants assigned to the waitlist control arm will be able to access the full SCP-R materials following completion of their final study tasks. Although 3 HCPs were nominated by more than one YBCS participant, each HCP only had participants in the same study arm.

YBCS outcome measures

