Hot flash frequency and severity over the prior 24 hours will be measured in each questionnaire and via daily via text messages using the following questions: "How many hot flashes have you had in the past 24 hours?" and "How many of your hot flashes in the past 24 hours would you categorize as mild, moderate, severe and/or very severe?" The hot flash score is calculated as the weighted sum of the number of hot flashes in each severity category multiplied by a severity-exclusive weight (1-mild, 2-moderate, 3-severe, 4-very severe). For the primary analysis, a decrease of 50% in the hot flash score will be defined as an improvement in hot flashes for the primary composite outcome. Secondary hot flash outcomes will include quality of life measured by the 29-item Menopause-specific Quality of Life (MENQOL) scale, confidence to talk with a HCP about hot flash management, plans to implement and implementation of a suggested tip from the intervention materials.

Fertility-related concerns will be measured with the Reproductive Concerns After Cancer Scale (RCAC), specifically fertility potential and pregnancy subscales. The RCAC is an 18-item multidimensional scale composed of 6 subscales (fertility potential, pregnancy, child's health, disclosure to partner of fertility status, personal health, acceptance of infertility) measuring reproductive health concerns of young adult female cancer survivors. The two subscales were chosen, because the SCP-R content addressed these constructs. Each subscale consists of 3 questions with response options ranging from 1 "Strongly disagree" to 3 "Neither agree nor

disagree" to 5 "Strongly agree". Scores for the fertility and pregnancy subscales will be calculated by averaging responses (range 1-5), scores > 3 indicating concern. For the primary analysis, scores \leq 3 in follow up will be considered an improvement in fertility-related concerns for the primary composite outcome. Secondary fertility-related outcomes will include the overall RCAC score, referral, consultation and treatment with a fertility specialist, pregnancy planning, and confidence to talk with a HCP about fertility-related concerns and plans to implement and implementation of suggestions from the fertility SCP.

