Contraception outcomes will be analyzed in participants at risk of unintended pregnancy, defined as having a uterus and at least one ovary, sexually active in the 24 months prior to or during the study, ≤ 45 years old. For the primary analysis, use of highly effective birth control methods (intrauterine devices, female sterilization, male partner sterilization, combined hormonal contraception, progestin implants or injections) during follow up will be considered an improvement for the primary composite outcome. Secondary contraceptive outcomes will include confidence to talk with a HCP about contraception, plans to implement and implementation of suggestions from the contraception SCP.

Sexual health will be measured the Vaginal Atrophy Symptoms Score, a 4-item scale on vaginal dryness, soreness, irritation and dyspareunia experienced in the prior 4 weeks [29]. Each item has a 4-point Likert scale response (0-none, 1-mild, 2-moderate, 3-severe). The scale will be summarized by averaging responses, with higher scores indicating a greater level of vaginal atrophy. For the primary analysis, a decrease of 50% in the score will be defined as an improvement in vaginal symptoms for the primary composite outcome. Secondary outcomes included sexual desire, arousal, orgasm and pain via the 19-item Female Sexual Function Inventory (FSFI), confidence to talk with a HCP about vaginal symptoms and sexual health management, plans to implement and implementation of a suggested tip from the intervention materials.

HCP measures

HCP preparedness and confidence in talking to their patients about each of the four reproductive health issues will be measured. Each preparedness item had a 4-point Likert scale response (very unprepared, unprepared, prepared, and very prepared). Each confidence item had a 7-point Likert scale response (not at all confident, slightly confident, somewhat confident, moderately confident, quite confident, very confident, and extremely confident). Demographic, medical specialty, and experience and volume of breast cancer patients, and satisfaction with SCP materials will also be measured.

YBCS participant adherence and retention

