To quantify intervention effects on each of the four reproductive health issues, we will also undertake secondary analyses to compare changes in each issue separately. As participant responses will be measured at enrollment, 12 and 24 weeks, we will compare each health issue outcome between the intervention and waitlist control groups using linear mixed effect models for the continuous outcomes (hot flash score, vaginal atrophy symptom score, fertility concerns score) and GEE models for binary outcomes (use of effective contraceptive method). Best linear unbiased predictors from the mixed models will also be used to impute missing outcomes for the primary composite outcome. Similar analysis will be conducted for secondary outcomes, which include additional YBCS-reported symptoms and actions, as well as healthcare provider preparedness and confidence.

Sample size

YBCS participants will be randomized into two arms: intervention and waitlist control. We will measure outcomes at enrollment, 12 weeks, and 24 weeks. Leveraging published data on hot flashes [31], we based sample-size calculations on detecting meaningful changes in hot flash frequency and score. With a sample size of 50/arm, there will be 80% power to detect a 0.57 effect-size between groups on hot flash score changes from baseline to 24 weeks based on a 2-sided t-test with alpha =0.05. This effect-size translates to a group difference of 1.2 hot flashes or 3 units in the hot flash score, if we assume the standard deviation of the change was 2 hot flashes or 5 score units per patient per day. Incorporating all the repeated measurements on each participant should ensure sufficient power to detect an even smaller effect size. In particular, assuming 2 post-randomization measures with autocorrelation 0.5, there is 80% power to detect a 0.44 effect size with 50 samples in each arm and 2-sided significance level 0.05.

Considering the composite primary outcome of improvement in at least 1 reproductive health issue, we have 80% power to detect a 27% group difference, e.g., 25% in the control arm and 52% in the treatment improve on at least one outcome. Given that some participants may have the same healthcare provider, we account for a clustering effect as follows: we assume as a worst-case scenario that on average 3 participants shared a provider, and that intraclass correlations (ICC) of the study outcomes due to a shared physician is 0.1. This results in a design

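### Two secondary action outcomes (fertility and contraception) are defined by a care plan that controls cannot open during follow-up, so their between-arm comparison is tilted toward the intervention

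*Combined protocol and SAP*

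**What the plan says.** Under YBCS outcome measures, the secondary fertility outcomes include "plans to implement and implementation of suggestions from the fertility SCP" and the secondary contraception outcomes include "plans to implement and implementation of suggestions from the contraception SCP". The hot flash and sexual health paragraphs use a different phrase, "plans to implement and implementation of a suggested tip from the intervention materials".

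The section on intervention prototype development and refinement describes four sections of content for each issue. The first is "a 1- to 2-page SCP framed in a question and answer format"; the fourth is the curated resource list. Access differs by arm: "The intervention arm will be able to access all 4 sections for all 5 issues", whereas "the waitlist control arm will only be able to access the list of curated web-based resources for all 5 issues". Under Blinding, the waitlist arm "will be able to access the full SCP-R materials following completion of their final study tasks".

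The Statistical Analysis section describes between-arm models (linear mixed models for continuous outcomes, GEE for binary ones) and then says: "Similar analysis will be conducted for secondary outcomes, which include additional YBCS-reported symptoms and actions". No section restricts the SCP-linked items to the intervention arm, rewords them for controls, or labels them as uptake or process measures.

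**The concern.** A between-arm comparison is informative only if a participant in either arm can score on the outcome by doing the same thing. The fertility and contraception items are tied to where the idea came from. Taken as written, a control who plans or takes a step that the SCP happens to recommend does not count, because she was never given the suggestion. The comparison then mixes two things: any real difference in behaviour, and the fact that one arm was handed the document.

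The plan presents SCP-R as a way to get women to take practical steps on their symptoms. A positive result on these two items would naturally be read as evidence that it does so. As defined, they could show a difference even if women in both arms behaved identically.

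**Working it through.** **Step 1. Can a control score on the item?** The relevant provisions, side by side:

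| Route to the fertility or contraception SCP | Intervention arm | Control arm before the 24-week outcome | Section |
|---|---|---|---|
| Website | All four sections, including the SCP | Resource list only | Intervention prototype development and refinement |
| Text messages | Reproductive health prompts | Study adherence messages | Website and text messaging platforms |
| Nominated HCP | Full intervention | Resource list only | Material and Methods |
| Delayed access | Not applicable | After the final study tasks | Blinding |

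No route supplies a control with the SCP before her outcomes are recorded. Read literally, her score on an item defined by SCP suggestions is zero. Read loosely, it is lower than her behaviour warrants.

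**Step 2. How large could the artefact be?** The plan states no figure to reproduce here and gives no action rates, so the rates below are assumptions.

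- Analysed women per arm: n = 50, the evaluable size in the Sample size section.
- Test level: two-sided 0.05, from the same section.
- True action rate q: equal in both arms, so there is no real effect.
- Share f of acting controls who still answer yes: 0 (literal reading) or 0.5 (loose reading).

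The intervention count is X ~ Binomial(n, q) and the control count is Y ~ Binomial(n, f·q). The spurious rejection rate is the sum of P(X = x)·P(Y = y) over all tables with Fisher p ≤ 0.05. Fisher's test stands in for the planned binary model because a logistic odds ratio has no finite estimate when one arm has no events.

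For f = 0 this has a simple form. With 50 per arm, 5 v 0 gives p = 0.056 and 6 v 0 gives p = 0.027, so the test rejects when X ≥ 6. At q = 0.10, P(X ≥ 6) = 0.384; at q = 0.20 it is 0.952.

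| True action rate, both arms | Controls score zero | Half of acting controls say yes | No artefact (f = 1) |
|---|---|---|---|
| 5% | 4% | 1% | 1% |
| 10% | 38% | 6% | 2% |
| 20% | 95% | 20% | 3% |
| 30% | over 99% | 35% | 3% |

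**Step 3. Fewer analysed women.** Contraception outcomes are restricted to women at risk of unintended pregnancy, so 50 per arm is probably too many for that item. With an assumed 25 per arm and controls at zero, 5 v 0 gives p just above 0.05 and 6 v 0 gives p = 0.022, so rejection again needs X ≥ 6. The rates are 3%, 38% and 81% at q = 10%, 20% and 30%.

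**Step 4. Which outcomes are outside the problem?** Specialist referral, consultation and treatment, and pregnancy planning, appear in the same list as the fertility item and name no source. Use of highly effective contraception is part of the primary composite and has its own GEE comparison. A control can score on all of these. The symptom scores do not refer to the SCP at all.

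**The case against.** The strongest reply is that the questionnaire wording is not in the documents. The outcome label may be shorthand for a list of behaviours drawn from the SCP and put to both arms in the same words. If so, controls can score and the bias largely disappears. This stands as a limit on certainty. It does not rescue the definition as written, and a definition that misdescribes the item still needs correcting.

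A second reply is that the plan uses its terms loosely. In the HCP procedures section, the phrase for intervention materials explicitly covers either the full SCP-R or the resource list alone, and HCPs are to be mailed or reminded of their patient's SCP with no split by arm. This stands for the hot flash and sexual health items, which refer to intervention materials: a control might score there, so those items are ambiguous, not shown to be biased. It does not carry over well to the fertility and contraception items, which name the SCP, a section that the plan's own description of the content separates from the resource list.

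Three stronger readings are tempting, and the documents do not support them:

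- A reader might infer that the plan has no fair measure of action. It does: the source-neutral outcomes in Step 4 already compare several key behaviours between arms.
- A reader might infer a false-positive rate near 100%. A very small p-value for one expected table (20/50 v 0/50 gives p = 1.8e-7) is not an error rate. The rate nears 100% only at action rates of about 20% or more with 50 per arm and controls at or near zero.
- A reader might infer that the items would unblind controls at 12 weeks. That requires the items to be asked then, to name the SCP, and to be understood by controls as something they lack. None of this is stated.

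**Conclusion.** The point holds for two secondary outcomes: the SCP-linked fertility and contraception items. As defined, their between-arm contrast partly measures receipt of the SCP, and the error runs in one direction, toward the intervention. The hot flash and sexual health items need clearer wording, but bias is not established for them. No conclusion about the primary composite, the symptom scores or the source-neutral action outcomes is affected.

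The size cannot be fixed from the documents. It depends on the true action rate, on how controls interpret the item and on the number analysed. Across the assumptions shown, spurious significance ranges from about the no-artefact level (rare actions, or a loose reading at low rates) to near certainty (action rates of 20% or more, 50 per arm, controls at zero). It should be corrected before these two outcomes are used to claim that SCP-R changes what women do, but it does not threaten the trial's main result.

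**What to change.** Define the between-arm action outcomes for each issue as a list of behaviours that does not name their source. Ask both arms the same items in the same words, recording for each whether it is planned and whether it has been done since enrollment, and compare arms on those. Use the same neutral wording for the hot flash and sexual health items, which removes their ambiguity.

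Keep implementation of a suggestion from the SCP as a descriptive uptake measure in the intervention arm only, asked after the other 24-week items.

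If the questionnaire already lists behaviours without naming the SCP, only the outcome definitions for fertility and contraception need correcting to say so.

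The cost is a few reworded or added check-boxes and matching edits to the outcome definitions. The between-arm difference will probably be smaller, but it can then be read as a difference in behaviour.

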YBCS are eligible if they report experiencing at least one of the four targeted reproductive health issues: hot flashes (\geq 4 per day with \geq 1 at least moderate in severity), moderate to high pregnancy and/or fertility concerns (fertility or pregnancy subscale score >3 on the Reproductive Concerns After Cancer Scale), not using contraception or using a less effective method (barrier or fertility awareness methods, withdrawal, or spermicides), or vaginal atrophy symptoms (\geq 1 symptom of vaginal dryness, irritation, soreness or dyspareunia over the past 4 weeks reported as at least moderate in severity). Additional eligibility criteria include: ages 18-50 at study enrollment, diagnosed with stage 0-III breast cancer between ages 18-45, completed primary cancer treatment including surgery, chemotherapy and radiation, are not pregnant at enrollment, are able to read English and access the Internet, and are able to complete daily text message hot flash diaries.

YBCS are recruited from the following sources: (1) cancer advocacy organizations including the Young Survival Coalition, Susan G. Komen San Diego and Army of Women-a program by the [name] Research Foundation, (2) referrals from health care providers and patient advocates, (3) Research Match, (4) previous observational studies conducted by the investigators. Interested YBCS are directed to the study web portal to create a secure personal account, followed by online access to study description, screening for eligibility and consent.

Consented participants complete the enrollment questionnaire and undergo a 7-day daily hot flash text message run-in period. Participants receive two daily text messages prompting them to report the number of hot flashes and severity of each hot flash (mild, moderate, severe, or very severe) in the previous 24 hours. Participants with at least 70% adherence over 7 days are then randomized.

YBCS randomization

Computerized, blocked randomization with equal allocation to intervention and waitlist control arms was undertaken. Randomization is stratified by the four a priori reproductive health issues in order to

maintain balance between the intervention and waitlist control groups with regard to these factors. Fifteen unique strata were created based on possible combinations of experiencing one or more of the four late effects.

HCP eligibility, recruitment, consent, enrollment and procedures

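### The contraception analysis set is named for unintended pregnancy but its definition omits pregnancy intention, so women trying to conceive at enrollment are scored as non-improvers unless they adopt a highly effective method

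*Combined protocol and SAP*

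**What the plan says.** All references are to the combined protocol and SAP.

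- **Analysis set (YBCS outcome measures, contraception paragraph).** Contraception outcomes are limited to "participants at risk of unintended pregnancy, defined as having a uterus and at least one ovary". The full definition is a closed list: "having a uterus and at least one ovary, sexually active in the 24 months prior to or during the study, ≤ 45 years old".
- **Scoring (same paragraph).** Use of a highly effective method "during follow up will be considered an improvement for the primary composite outcome". The composite definition under Statistical Analysis likewise counts use of such methods. Neither place has a rule for women who are trying to conceive or who conceive during follow-up.
- **Entry (YBCS eligibility, recruitment, consent and enrollment).** A woman has the contraception issue if she is "not using contraception or using a less effective method (barrier or fertility awareness methods, withdrawal, or spermicides"). No reason for non-use is asked. The only pregnancy-related exclusion is that participants "are not pregnant at enrollment".
- **Fertility issue.** Women may also enter through "moderate to high pregnancy and/or fertility concerns". The secondary fertility outcomes include "referral, consultation and treatment with a fertility specialist, pregnancy planning".
- **Overlap (YBCS randomization).** The fifteen strata are the possible combinations of the four issues, so one woman can have both the fertility and the contraception issue.
- **Separate analysis (Statistical Analysis).** Each issue is also compared between arms on its own. Use of effective contraception is analyzed by GEE as a binary outcome.

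**The concern.** The name of the set and its content do not match. Being at risk of an unintended pregnancy depends on what the woman intends, and intention is the one thing the definition leaves out. An analyst who follows the list will include women who use no method because they want a pregnancy. An analyst who follows the name will leave them out. The two would report different results from the same data.

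This trial is more exposed than most. It recruits partly on fertility and pregnancy concerns, and the intervention arm receives full content on both fertility and contraception. Some participants may well be trying to conceive. For them the contraception outcome can show improvement only through a step that runs against their own goal, while pregnancy planning and fertility treatment are recorded elsewhere as fertility outcomes.

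What is at stake is mainly the contraception-specific estimate: whether it describes the population it names, and how far it is diluted.

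**Working it through.** **1. The plan's own figure.** The plan gives no expected rate, effect size or power for the contraception outcome. Its nearest figure is the composite power under Sample size: 80% for 25% v 52%. Taking 50 per arm and two-sided alpha 0.05 from the hot flash calculation in the same section:

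- mean proportion = (0.25 + 0.52)/2 = 0.385
- standard error under no difference = √(2 × 0.385 × 0.615/50) = 0.0973
- standard error under the alternative = √((0.25 × 0.75 + 0.52 × 0.48)/50) = 0.0935
- power = Φ((0.27 − 1.96 × 0.0973)/0.0935) = Φ(0.85) = 80.2%

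The stated figure reproduces, and the present point does not alter it.

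**2. One woman followed through the rules.** Take a woman aged 45 or under, with a uterus and an ovary, sexually active, not pregnant, and using no contraception because she is trying to conceive.

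| Rule | Result |
|---|---|
| Contraception issue at entry | Met, since non-use counts whatever the reason |
| Pregnancy exclusion | Does not apply |
| At-risk definition | Met on anatomy, sexual activity and age |
| Improvement | Only if she adopts a highly effective method |
| She conceives in follow-up | No rule, so not improved |

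Nothing elsewhere in the document removes her.

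**3. Dilution of the contraception-specific comparison.** Let f be the share of the set who are trying to conceive and do not adopt a highly effective method, equal in both arms. Let pI and pC be the adoption rates among the other women.

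- Observed rates: (1 − f)pI and (1 − f)pC
- Observed difference: (1 − f)(pI − pC)

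The documents do not give f. Over an assumed range:

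| Assumed f | Factor | Shrinkage of the difference |
|---|---|---|
| 10% | 0.90 | 10% |
| 20% | 0.80 | 20% |
| 30% | 0.70 | 30% |

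The factor applies to the difference in proportions. The ratio of the two proportions does not change, and an odds ratio above 1 moves toward that ratio.

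**4. A possible difference between arms.** Suppose the fertility content leads a further share d of the set, in the intervention arm only, to pursue pregnancy, and suppose these women would otherwise have adopted at rate pI. The observed difference becomes (1 − f)(pI − pC) − d × pI. The extra term lowers the estimate, and randomization does not cancel it because it arises after allocation. The documents give no value for d, and whether it exceeds zero is unknown.

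**The case against.** **The name already excludes these women.** One could say that the word unintended settles the matter. It does not, because the plan goes on to define the term and the definition has no such criterion.

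**The bias is limited.** Stratified randomization should spread these women about evenly, so the expected result is dilution and not imbalance. That stands. Downward bias beyond dilution needs the intervention to increase attempts to conceive, which is possible but not shown.

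**The range for f is assumed.** This also stands. The 10% to 30% shrinkage restates the assumption through (1 − f) and is not an estimate.

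**Stronger readings the documents do not support.**

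- A reader might infer that contraception scoring works against the fertility component of the primary endpoint. In the composite, that component is a low score on the two concern subscales, not conception. Lower concern and effective contraception are compatible. The tension is with the secondary fertility outcomes, for which no favorable direction is stated.
- A reader might infer that women who enter only through contraception are near-certain composite failures. To enter that way only, both concern subscales must be 3 or below. The follow-up criterion (3 or below under YBCS outcome measures, below 3 under Statistical Analysis) is not expressly limited to women with concern at baseline. Read literally, such a woman could count as improved on fertility by keeping a low score.
- A reader might infer a loss of composite power. If 5% of each arm had no other route to improvement, the rates would be 0.95 × 25% = 23.75% and 0.95 × 52% = 49.4%, with power 77%. At 10% they would be 22.5% and 46.8%, with power 73%. But those shares appear nowhere in the documents. The 25% v 52% pair is an example for the whole trial population, and nothing says it excludes these women, so the reduction may count them twice. Leaving them out (47.5 or 45 per arm at 25% v 52%) gives 78% and 76%, a gain of only about 1 to 3 points.

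**Conclusion.** The point holds for the contraception analysis set. As written, the rule includes women trying to conceive at enrollment and scores them as non-improvers unless they take up a highly effective method, so the set does not match the population it is named for. In the separate contraception GEE, the arm difference shrinks by (1 − f). This assumes that f is equal in both arms and that none of these women adopt such a method. The size of f is unknown. Any rise in attempts to conceive caused by the intervention would lower the estimate further.

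For the primary composite the effect is likely small, since improvement on any one issue makes a woman a responder. The documents support no figure for lost power. The case for change rests on a clear definition and an interpretable contraception estimate.

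**What to change.** 1. Add to the at-risk definition under YBCS outcome measures: *and not trying to conceive or planning pregnancy during the 24 weeks, as reported at enrollment*.
2. Use enrollment answers only, so that this criterion is fixed before randomization. Pregnancy planning is already a listed outcome, but the plan does not say whether it is asked at enrollment. If it is not, add one item. Follow-up answers should not stand in for it, because the intervention may change them.
3. Apply the same criterion to the contraception issue in the eligibility and randomization sections, so that no woman is randomized on an issue on which she cannot be scored. Changing the analysis set alone would leave women whose only issue is contraception in the trial with no qualifying issue.
4. State that any such woman already randomized stays in the intent-to-treat composite and is left out only of the contraception-specific analysis.
5. State how a pregnancy during follow-up is scored. The enrollment criterion does not remove women whose intention changes after randomization, so the report should show pregnancy planning by arm beside the contraception result.

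The cost is at most one enrollment question and wording in three sections, with a somewhat smaller contraception analysis set and slightly fewer women eligible by that route. The definition should be settled before outcomes are seen by arm.
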